## OTHER CYCLES (WEEKLY (QW) DOSING)

Trial Period	Protocol section	Treatment b (28- day cycles)						Post-Treatment		
		Cycle X (Weekly Dosing)					Disease Assessment	End of Treatment (EOT)	30-Day Safety Follow-Up bb	Survival Follow-Up cc
Visit Day		Day 1	Day 2 (Cycle 3 Only)	Day 3 (Cycle 3 Only)	Day 8	Day 15	Day 22			
Scheduling Window (Days)		+ 7 days			+1 day	+1 day	+1 day	± 3 days	± 2 weeks	Every 2 Months
ADMINISTRATIVE PROCEDURES										
Prior/Concomitant Medications f	8.4	X								
PRBC and platelet transfusion documentation	8.4	X								
Post-Treatment Cancer Therapy	8.5							X	X	X
Survival Status	7.5.2	X								
CLINICAL PROCEDURES										
Administer NC525 c,s	5.2.2	X			X	X	X			
Comprehensive PEG g	8.6.2.1							X		
Targeted physical assessment h	8.6.2.2	X			X	X	X			
Vital signs and weight i	8.6.4	X	X	X	X	X	X	X		
ECOG performance	8.6.3	X			X	X	X			
12-lead ECG j	8.6.7									
AE assessment k	9.1	X								
LOCAL LABORATORY										
Hematology with differential	Table 8	X n	X	X	X n	X n	X n	X	X	
Comprehensive CMP	Table 8	X n	X	X	X n	X n	X n	X	X	
Coagulation panel	Table 8	X n			X n	X n	X n			
Inflammatory Markers	Table 8	X								
Pregnancy Test	Table 8	X r			X r	X r	X r		X q	
Bone Marrow Aspirate and Biopsy Local Disease	Table 10							X z	X dd	X ee

Trial Period	Protocol section	Treatment b (28- day cycles)						Post-Treatment		
		Cycle X (Weekly Dosing)					Disease Assessment	End of Treatment (EOT)	30-Day Safety Follow-Up bb	Survival Follow-Up cc
Visit Day		Day 1	Day 2 (Cycle 3 Only)	Day 3 (Cycle 3 Only)	Day 8	Day 15	Day 22			
Scheduling Window (Days)		+ 7 days			+1 day	+1 day	+1 day	± 3 days	± 2 weeks	Every 2 Months
CENTRAL LAB										
Pharmacokinetics (PK) t	Table 9	X t	X t	X t						
Anti-Drug Antibodies (ADA) u	Table 9	X u							X u	
Cytokines w	Table 9	X w								
Bone Marrow Immunophenotyping v	Table 10							X		
Bone Marrow Aspirate and Biopsy (Smear, Touch Prep, or FFPE) p	Table 10							X		

## OTHER CYCLES (BI-WEEKLY (Q2W) DOSING)

Trial Period	Protocol section	Treatment b (28- day cycles)					Post-Treatment		
		Cycle Y (Biweekly Dosing)			Disease Assessment	End of Treatment (EOT)	30-Day Safety Follow-Up bb	Survival Follow-Up cc	
Visit Day	Day 1	Day 2 (Cycle 3 Only)	Day 3 (Cycle 3 Only)	Day 15	Every 3 Cycles or at suspected PD				
Scheduling Window (Days)	+ 7 days			+1 day	± 7 days			Every 2 Months	
ADMINISTRATIVE PROCEDURES									
Prior/Concomitant Medications f	8.4	X							
PRBC and platelet transfusion documentation	8.4	X							
Post-Treatment Cancer Therapy	8.5						X	X	X
Survival Status	7.5.2	X							
CLINICAL PROCEDURES									
Administer NC525 s	5.2.2	X			X				
Comprehensive PEG g	8.6.2.1						X		
Targeted physical assessment h	8.6.2.2	X			X	X			
Vital signs and weight i	8.6.4	X	X	X	X	X	X		
ECOG performance	8.6.3	X			X				
12-lead ECG j	8.6.7								
AE assessment k	9.1	X							
LOCAL LABORATORY									
Hematology with differential	Table 8	X n	X	X	X n	X	X		
Comprehensive CMP	Table 8	X n	X	X	X n	X	X		
Coagulation panel	Table 8	X n			X n				
Inflammatory Markers	Table 8	X							
Pregnancy Test	Table 8	X r			X r		X q		
Bone Marrow Aspirate and Biopsy Local Disease	Table 10					X aa	X dd		X ee

Trial Period	Protocol section	Treatment b (28- day cycles)				Post-Treatment		
		Cycle Y (Biweekly Dosing)			Disease Assessment	End of Treatment (EOT)	30-Day Safety Follow-Up bb	Survival Follow-Up cc
Visit Day	Day 1	Day 2 (Cycle 3 Only)	Day 3 (Cycle 3 Only)	Day 15	Every 3 Cycles or at suspected PD			
Scheduling Window (Days)	+ 7 days			+1 day	± 7 days		± 2 weeks	Every 2 Months
Assessment (Flow Cytometry, Cytogenetics, Morphology)								
CENTRAL LAB								
Pharmacokinetics (PK) t	Table 9	X t	X t	X t				
Anti-Drug Antibodies (ADA) u	Table 9	X u				X u		
Cytokines w	Table 9	X w						
Bone Marrow Immunophenotyping v	Table 10				X			
Bone Marrow Aspirate and Biopsy (Smear, Touch Prep, or FFPE) p	Table 10				X			

- a. Written consent must be obtained prior to performing any protocol-specific procedure. Results of a test performed prior to the subjects signing consent as part of routine clinical management are acceptable in lieu of a screening test if performed within the specified time frame (e.g., within 7 days prior to the first dose of trial treatment).
- b. Treatment cycles will begin every 28 days (+ 1 day window for weekly dosing schedule and + 7-day visit window for biweekly dosing schedule).
- c. NC525 will be administered every week during Cycles 1 and 2 on Day 1, Day 8, Day 15, and Day 22. Subjects, may continue weekly (QW) dosing until overall response is achieved (e.g., CR, CRi, CRh), at which time they may switch to biweekly (Q2W) dosing. For biweekly dosing, NC525 will be administered every two weeks on Days 1 and 15 of each cycle.
- d. All subjects will be required to receive prophylaxis for TLS beginning on Day -1 of Cycle 1. Refer to [Section 5.8.3](#) for more details on TLS Prophylaxis and [APPENDIX 5 – Recommendations for Initial Management of Electrolyte Imbalances and Prevention of Tumor Lysis Syndrome \(TLS\)](#) for further information.
- e. Medical history will include relevant medical or surgical treatment within the last 10 years considered to be clinically significant by the investigator.
- f. Any prior medication received up to 21 days before the first dose of study drug should be recorded. All concomitant medications received up to 30 days after the last dose of study intervention should be recorded. Upon discontinuation of study treatment, only post-anticancer treatments and concomitant medications and procedures related to adverse events (including SAEs and ECIs) should be recorded. Please also refer to [Sections 5.11.1](#) for details on prohibited and restricted medications.
- g. Comprehensive Physical examinations must be performed by a medically qualified individual such as a licensed physician, physician's assistant, or an advanced registered nurse practitioner, as local law permits. The comprehensive physical examination should include assessment(s) of the following organ or body systems: skin; head, eyes, ears, nose, and throat; thyroid; lungs; cardiovascular system; abdomen (liver, spleen); extremities; and lymph nodes, as well as a brief neurological examination.
- h. Targeted physical examination will be a symptom-directed evaluation conducted by the investigator or a medically qualified designee. Notable abnormalities that are considered clinically significant in the judgment of the investigator are to be reported as AEs.
- i. During Cycle 1, vital signs (blood pressure, pulse, respiratory rate, and body temperature) will be assessed pre-dose, at the end of infusion of study treatment (+10 minutes), and every 60 minutes  $\pm$  10 minutes thereafter for 2 hours or per PI discretion. At subsequent cycles, vital signs will be assessed pre-dose and at the end of infusion (+10 minutes) of study treatment. Additional vital signs may be collected per PI's discretion if indicated.
- j. A standard 12-lead electrocardiogram (ECG) will be performed one time during screening using local standard procedures. Clinically significant abnormal findings should be recorded as medical history. Additional time points may be performed as clinically necessary at the discretion of PI.
- k. All AEs, SAEs and other reportable safety events that occur after the consent form is signed but before first study treatment must be reported by the investigator if they cause the subject to be excluded from the study or are the result of a protocol-specified intervention, including but not limited to washout or discontinuation of usual therapy, or a procedure. From the time of first study treatment through 30 days following cessation of treatment, all adverse events must be reported by the investigator. SAEs and ECIs will be collected for 90 days after the end of treatment or 30 days after the end of treatment if the subject initiates new post-treatment cancer therapy, whichever is earlier. .
- l. Laboratory tests for screening are to be performed within 7 days prior to the first dose of study treatment.
- m. Local Laboratory samples on Cycle 1 Day 1 must be performed before the administration of any study treatment and should be reviewed by the investigator or designee and found to be acceptable prior to the administration of study drug.
- n. On the day of study drug administration for all subsequent study treatments, pre-dose laboratory procedures can be conducted up to 72 hours before administration of study treatment. Local lab results should be reviewed by the investigator or qualified designee and found to be acceptable before treatment is initiated.
- o. Urinalysis to be performed at Screening. Urine dipstick – if abnormal, perform microscopic urinalysis. Additional time points may be performed as clinically necessary at the discretion of PI.
- p. Bone Marrow aspirate (smear, touch prep, or FFPE) will be sent to the Central Lab for retrospective central lab response analysis. Please refer to the Central Lab Manual for processing instructions.
- q. The serum pregnancy test performed at screening must be performed within 72 hours before the first dose of study drug. Serum pregnancy will also be performed at EOT.
- r. For women of child-bearing potential only, urine pregnancy must be performed within 72 hours prior to study treatment and resulted before study drug administration. If positive, confirm results with serum pregnancy test.
- s. During Cycle 1 Day 1, subjects will be required to stay at the study site for safety observation for 48 hours after administration of NC525 infusion. For all subsequent doses subjects will be required to be observed for 1 hour post NC525 infusion or per PI discretion. After Cycle 1 Day 1, NC525 may be administered in an outpatient setting per investigator discretion.
- t. Refer to [Table 9](#) for PK collection timepoints throughout the study.
- u. Refer to [Table 9](#) for ADA collection timepoints throughout the study.
- v. Immunophenotyping (Bone Marrow) will be performed per [Table 10](#). Please refer to the Central Lab Manual for instructions.
- w. Refer to [Table 9](#) for Cytokine collection timepoints throughout the study.

- x. Historical bone marrow aspirates at screening will not be accepted, a bone marrow aspirate and biopsy must be performed for study entry to collect mandatory biomarker assessments.
- y. Bone marrow aspirate and biopsy at Cycle 1 Day 14 is optional. If it is performed, immunophenotyping sample should also be collected.
- z. Bone marrow aspirate and biopsy at the end of Cycle 1 must be performed prior to administration of Cycle 2. Bone marrow aspirate and biopsy at the end of Cycle 2 must be completed within 3 days prior to Cycle 3 Day 1. Local Disease Assessments must be reviewed by the investigator or qualified designee and found to be acceptable prior to the administration of study drug for Cycle 3. Bone marrow aspirate and biopsies should continue to be collected every 28 days during QW dosing schedule.
- aa. All other subsequent bone marrow aspirate and biopsy collections during Q2W dosing, must be performed every 3 cycles ( $\pm$  7 days) and upon concern for progressive disease.
- bb. A Safety Follow-Up Visit should be performed for all subjects approximately 30 days following discontinuation of study drug and then as clinically appropriate for safety assessment. The subject should be followed until a satisfactory clinical resolution of any adverse event is achieved. The Safety Follow-up may be performed by phone.
- cc. Following the 30-day Safety Follow-up Visit, subjects should be followed approximately every 2 months to assess for survival status. For subjects who discontinue study drug for reasons other than disease progression, hematology and disease assessment data (per standard of care) will continue to be collected until PD or initiation of a new post-treatment cancer therapy. Updated survival status may be requested by the Sponsor at any time during the course of the study. Upon Sponsor notification, all subjects who do not/will not have a scheduled study visit or study contact during the Sponsor defined time period will be contacted for their survival status (excluding subjects that have a death event previously recorded).
- dd. Collect only if no bone marrow has been collected within last 6 – 8 weeks, or if relapse of disease has already been confirmed.
- ee. If Bone Marrow is collected per SOC, results should be recorded during the survival follow-up period until the subject discontinues the study.

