### 3.2.2. Dose Levels and Cohorts

The Dose Escalation part of the study will begin the following planned dose levels and cohorts:

- **Dose Level 1:** 2 mg/kg biweekly\*\*
- **Dose Level 2:** 2.5 mg/kg\* weekly\*\*
- **Dose Level 3:** 4.5 mg/kg weekly\*\*
- **Dose Level 4:** 10 mg/kg weekly\*\*
- **Dose Level 5:** 20 mg/kg weekly\*\*
- **Dose Level 6:** 30 mg/kg weekly\*\*

\*\* Cohort 1: Biweekly (Q2W) for Cycles 1 through 6 followed by every 4 weeks (Q4W) thereafter. Cohort 2 and above: Weekly (QW) dosing for Cycles 1 and 2. Subjects may continue QW dosing until overall response (e.g., CR, CRh, or CRi) is achieved, at which time they may switch to Q2W dosing.

The planned dose levels for Dose Escalation include a maximum dose increment of less than a half-log (233%) between each dose level. Using the Escalation/De-escalation Rules governed by the BON design, if criteria is met allowing dose escalation, the subsequent dose level will first be evaluated against the Dose Increment Modification Rules For Dose Escalation ([Table 2](#)) taking into consideration the number of adverse events (Grade  $\geq 2$ ) and dose limiting toxicities which occurred at the current dose level prior to selecting the next dose.

In the event a dose increment modification is indicated during the Dose Escalation phase of the study, an ad-hoc safety meeting will occur with the Clinical Study Team to review the adverse event(s) against the qualifying criteria before any dose modifications are made.

All Adverse Events (excluding AEs unequivocally due to the underlying disease or an extraneous cause) occurring during the DLT Observation Period will be evaluated against the Dose Increment Modification rules, as follows:

- Limit the maximum dose increment to 100% if patients of a given cohort experience one Grade  $\geq 2$  AE (except for AEs unequivocally due to the underlying disease or an extraneous cause) during the DLT period.
  - *Example: If one  $\geq$  Grade 2 AE occurs in Dose Cohort 1 (2mg/kg), the subsequent dose level will be increased by 100% (4mg/kg) instead of the originally planned dose of 4.5mg/kg.*

- Limit the maximum dose increment to 50% if patients of a given cohort experience two or more Grade  $\geq 2$  AEs (except for AEs unequivocally due to the underlying disease or an extraneous cause) during the DLT period.

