## **8.6. Clinical Assessments and Procedures**

### **8.6.1. Adverse Event Monitoring**

Subjects will be instructed to report all AEs during the study and will be assessed for the occurrence of new or worsening AEs throughout the study. In order to avoid bias in eliciting AEs, subjects will be asked general, nonleading questions such as "How are you feeling?". All AEs (serious and nonserious) must be recorded on the source documents and eCRFs regardless of the assumption of a causal relationship with the study drug. The definition, reporting, and recording requirements for AEs are described in [Section 9.1](#).

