## **9. SAFETY MONITORING AND REPORTING**

### **9.1. Adverse Events (AEs)**

#### **9.1.1. Adverse Event Definition**

For the purposes of this protocol, an AE is defined as any untoward medical occurrence associated with the use of a drug in humans, whether considered drug related, that occurs after a subject provides informed consent and through the follow-up period. Both nonserious and serious AEs (SAEs) will be monitored throughout the study.

A pre-treatment event (PTE) is one that occurs after the time of informed consent (e.g., during the screening process) but prior to study drug administration. PTEs directly related to a study test or procedure should be reported during the Screening period.

Conditions that were already present at the time of informed consent should be recorded on the Medical History form in the eCRF.

Abnormal laboratory values or test results occurring after informed consent constitute AEs only if they induce clinical signs or symptoms, are considered clinically meaningful, require therapy (e.g., hematologic abnormality that requires transfusion), or require changes in the study drug(s).

Progression of the cancer under study is not considered an adverse event unless it results in hospitalization or death.

Hospitalization of a subject to allow for observation and management (e.g., IV hydration) for the purpose of TLS prophylaxis will not be captured as an SAE unless there is an additional reason for hospitalization or an additional criterion for seriousness other than hospitalization is met.

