#### **9.1.7. Time Period and Frequency for Collecting AE, SAE, and Other Reportable Safety Event Information**

All AEs, SAEs, and other reportable safety events that occur after the consent form is signed but before first study treatment must be reported by the investigator *if they cause the subject to be excluded from the study or are the result of a protocol-specified intervention*, including but not

limited to washout or discontinuation of usual therapy, diet, or a procedure. SAEs and ECIs will be collected for 90 days after the end of treatment or 30 days after the end of treatment if the subject initiates new post treatment cancer therapy, whichever is earlier.

All AEs from the time of first study treatment through 30 days following cessation of study treatment must be reported by the investigator.

All SAEs or ECIs, from the time of first study treatment through 90 days following cessation of study treatment, or 30 days following cessation of study treatment if the subject initiates new post-treatment cancer therapy, whichever is earlier must be reported by the investigator.

All pregnancies and exposure during breastfeeding, from the time of first study treatment through 90 days following cessation of study treatment, or 30 days following cessation of study treatment if the subject initiates new post-treatment cancer therapy must be reported by the investigator.

Additionally, any SAE brought to the attention of an investigator at any time outside of the time period specified above must be reported immediately to the Sponsor if the event is considered to be study drug related.

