#### 10.3.1.1. Adverse Events

A treatment-emergent adverse event (TEAE) is any AE either reported for the first time or worsening of a pre-existing event after the first dose of study drug. Analysis of AEs will be limited to TEAEs, but data listings will include all AEs regardless of their timing to study drug administration. Adverse events will be tabulated by the MedDRA preferred term and system organ class. Severity of AEs will be based on the NCI CTCAE v5.0 using Grades 1 through 5.

The subset of AEs considered by the investigator to have a relationship to study drug will be considered treatment-related AEs (TRAEs). If the investigator does not specify the relationship of the AE to study drug, then the AE will be considered treatment related. The incidence, frequency, duration, and severity of all AEs (regardless of causality) will be tabulated.

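### Recording rules conflict for events that begin between consent and first dose, and the TEAE definition turns on first report rather than onset, so an unworsened screening-onset event can be counted as treatment-emergent

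*Combined protocol and SAP*

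**What the plan says.** Three places restrict what must be reported before dosing.

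- Table 7, footnote k: events after consent but "before first study treatment must be reported by the investigator if they cause the subject to be excluded from the study", or if they result from a protocol-specified intervention.
- Section 9.1.7 applies the same two conditions to events "that occur after the consent form is signed but before first study treatment must be reported by the investigator".
- Section 9.1.1 defines a pre-treatment event, but its reporting instruction covers one kind: "PTEs directly related to a study test or procedure should be reported during the Screening period". For Medical History it says: "Conditions that were already present at the time of informed consent should be recorded on the Medical History form in the eCRF".

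Two places point the other way.

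- Section 8.6.1: "All AEs (serious and nonserious) must be recorded on the source documents and eCRFs regardless of the assumption of a causal relationship".
- Section 9.1.6 has AEs sought by open questioning from ICF signing onward, with a grade and start and end dates for each.

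Section 10.3.1.1 defines a TEAE as "any AE either reported for the first time or worsening of a pre-existing event after the first dose of study drug". AE analysis is restricted to TEAEs, while listings cover all AEs whenever they occurred. Primary endpoint 1 (Section 2.2.1) is how often AEs occur, how long they last and how severe they are.

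Section 3.2.2 governs the size of the next dose step through the increment rules in Table 2: "All Adverse Events (excluding AEs unequivocally due to the underlying disease or an extraneous cause) occurring during the DLT Observation Period will be evaluated".

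**The concern.** Screening lasts about 21 days (Sections 3.5 and 7.1) in people with relapsed or refractory myeloid disease, so some will develop a new clinical event in that time. Suppose such an event neither excludes the subject nor comes from a study procedure. One set of sections does not require it to be reported; another does. If a site follows the narrower rule, the event has no AE record and no grade when dosing starts.

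From first treatment onward all AEs must be reported, and Table 7 schedules a targeted examination on Day 1 whose clinically significant findings are to be reported as AEs. The event may then be reported for the first time after dosing. The TEAE definition has no onset condition, so its first limb is met even if nothing has worsened.

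At stake is the descriptive safety profile for primary endpoint 1. The study has no control arm, and Section 3.3 allows comparison only with the pretreatment state, so that profile depends on a sound pre-dose record.

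**Working it through.** The plan states no figure that depends on these rules, so there is nothing to reproduce. The check sets the provisions side by side and then illustrates scale.

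**1. Which events are affected.**

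| Onset | Record before first dose | TEAE if unworsened and still present? |
|---|---|---|
| Before consent | Medical History (9.1.1) | No |
| Consent to first dose; causes exclusion or comes from an intervention | Must be reported (footnote k, 9.1.7) | No |
| Consent to first dose; neither condition met | Not required by footnote k, 9.1.7 or 9.1.1; required by 8.6.1 and sought under 9.1.6 | Yes, on a literal reading, if first reported after dosing |
| On or after first dose | Must be reported | Yes, correctly |

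Only the third row is at issue.

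**2. Whether collected start dates cure it.** Only in part. Section 9.1.6 makes each change of severity a separate AE record, starting on the day of change. A screening-onset Grade 3 event that improves to Grade 2 after dosing produces a Grade 2 record with a post-dose start date. Without a recorded pre-dose grade, that improvement cannot be told from a new event.

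**3. Scale for the AE tables (inputs assumed).** Let p be the true on-treatment incidence of an AE term. Let q be the share of subjects with a same-term event that began between consent and first dose, was still present, and was first recorded after dosing. Taking the two as independent:

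observed incidence = p + q(1 − p)

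| q | Observed at p = 30% | Extra subjects of 14: 14 × q × 0.7 | Extra subjects of 63: 63 × q × 0.7 |
|---|---|---|---|
| 2% | 31.4% | 0.2 | 0.9 |
| 5% | 33.5% | 0.5 | 2.2 |
| 10% | 37.0% | 1.0 | 4.4 |
| 20% | 44.0% | 2.0 | 8.8 |

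Across the same range of q, the rise is 1.8 to 18 percentage points at p = 10% and 0.8 to 8 points at p = 60%. The denominators are the expansion size per dose (14) and the planned total (63).

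**4. Which dose decisions could be touched.** DLTs are judged against Table 6 from Cycle 1 Day 1 (Section 5.9.1). The expansion stopping rule also uses Table 6, with stated exclusions (Section 10.2.2). Neither refers to TEAEs. The Table 2 counts do not use the TEAE definition either; they turn on whether an event occurs in the DLT period. An event with earlier onset counts only if being present in that period is read as occurring in it.

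If it were so read, the planned per-dose steps are 2 to 2.5 (+25%), 2.5 to 4.5 (+80%), 4.5 to 10 (+122%), 10 to 20 (+100%) and 20 to 30 mg/kg (+50%). The 100% cap for one Grade ≥2 AE is below the planned step once (+122%). The 50% cap for two or more is below it three times (+80%, +122%, +100%). With q now taken as the share carrying a Grade ≥2 event of this kind, the chance of at least one such subject among 3 is 1 − (1 − q)³: 5.9%, 14.3%, 27.1% and 48.8% for q = 2%, 5%, 10% and 20%.

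**The case against.** The best defence is that the narrower sections say what must be reported, not that nothing else may be recorded. Section 9.1.1 starts the AE definition at consent. Sections 8.6.1 and 9.1.6 call for full recording with start dates, and the listings in Section 10.3.1.1 presuppose pre-dose AEs in the database. Section 8.3.1 collects current illnesses and all active conditions at screening, which Section 7.1 defines as the whole interval up to treatment. The TEAE wording mentions worsening of a pre-existing event separately, so an unworsened one is arguably outside it. Further detail is deferred to a supplemental SAP.

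Much of this stands, and it rules out several stronger readings:

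- **Such events are recorded nowhere.** A reader might infer this from footnote k, but the sections above point to recording. What is shown is a conflict, not a certain gap.
- **Only laboratory values have a Day 1 baseline.** Vital signs are taken pre-dose, and ECOG status and a targeted examination are scheduled on Day 1. None of these supplies an AE grade, however.
- **Most cohorts of 3 would be affected.** Assume 0.1 to 0.4 Grade ≥2 events per subject-week lasting a mean of 7 to 14 days. Then (r/7) × d × (1 − exp(−21/d)) gives 0.10 to 0.62 ongoing events per subject at first dose. Treating a cohort of 3 as Poisson, the chance of at least one event is 25% to 85%, and of two or more 3% to 56%. The rates have no source in the documents, and the calculation takes every such event as unrecorded, so these figures are ceilings under assumed inputs.
- **Dose escalation is distorted.** DLT decisions do not depend on the TEAE definition. For Table 2, events clearly due to disease or an outside cause are exempt, and an ad-hoc safety meeting reviews events before any change.

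Eligibility also removes some cases: exclusion 9 limits unresolved prior-therapy toxicity and exclusion 19 bars uncontrolled infection. Appendix 1 lets an investigator who knows the event began before dosing call it unrelated, which limits any effect on treatment-related tables.

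What the defence does not remove is that two recording rules coexist, the TEAE definition lacks an onset condition, and a later SAP cannot recover a pre-dose grade that was never collected.

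**Conclusion.** The point holds in limited form. Recording of events with onset between consent and first dose is governed by provisions that conflict. Because a TEAE is defined by first report or worsening, such an event can be counted as treatment-emergent if it was not recorded before dosing, even when it did not worsen. Any resulting bias in AE incidence is upward and falls on the descriptive tables for primary endpoint 1.

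The size is unknown. The range shown (30% read as 31.4% to 44.0%) rests on an assumed q of 2% to 20% and on independence. Inflation is possible, not demonstrated. The documents do not support extending the point to conditions present at consent, to DLT-based escalation or to the expansion stopping rule. The Grade ≥2 counts in Table 2 are open only through one reading of when an event occurs, and the plan does not say which reading applies. The change is worth making because it is cheap now and the missing grades cannot be reconstructed later.

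**What to change.** 1. Reconcile Table 7 footnote k and Sections 9.1.1 and 9.1.7 with Sections 8.6.1 and 9.1.6. Every event with onset from consent to first dose should be recorded, as a pre-treatment event or as medical history, with its onset date and its CTCAE grade at Cycle 1 Day 1 before dosing. Expedited reporting need not change.
2. In Section 10.3.1.1, define a TEAE as an event with onset on or after first dose, or one that worsens above its pre-dose grade. Onset should mean the start of the episode, not the start date of a record opened by a severity change.
3. Have the sponsor state whether events with pre-dose onset that do not worsen count toward the Grade ≥2 totals in Table 2. The choice of dose rule is the sponsor's; the text needs only to be unambiguous.

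The cost is protocol and eCRF wording and a few extra entries per subject over about 21 days.
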